**Describe the statistical method(s) that will be used to analyze the primary outcome(s) or endpoints:**

t-tests with Bonferroni corrections, or Wilcoxon rank sum tests if the distributions fail the Lilliefors test for normality.

**If appropriate describe secondary or post hoc analyses of primary outcome(s) or other exploratory analysis and if necessary, provide a breakdown of the methods used per outcome or endpoint:**

The effect of treatment on each outcome measure will be assessed using a repeated-measures ANOVA

---

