### Background & Purpose of Research

## Describe the purpose, specific aims or objectives and specify the hypotheses or research questions to be studied:

For this study, we hypothesize that use of movable wheelchair arm rest device during inpatient therapy will lead to significantly greater improvements in UE motor recovery than conventional treatment. (For a demonstration video of the movable wheelchair arm rest device, please visit: <https://youtu.be/RfbaOGhJfug>). Our Aim is to perform a randomized controlled trial of the movable wheelchair arm rest device with inpatients with subacute stroke in three different inpatient rehabilitation facilities (N=58; Months 6-24). UCI will be one of the study sites. Rancho Los Amigos Rehabilitation center and Casa Colina Hospital and Centers for Healthcare will potentially be the other two study sites. We are in the process of negotiating the contracts between sites. Participants will be >3 days and <3 weeks post-stroke, with initial FM scores <4239. Participants will be randomized to receive the movable wheelchair arm rest device or an electronic exercise program and instructed to practice moving their arm between therapy sessions. The primary outcome measure will be change in FM score from baseline to three-months post-stroke. We hypothesize that participants who receive movable wheelchair arm rest device will have significantly greater improvements in FM score than control ( $p < 0.05$ , RM-ANCOVA) without an increase in pain or spasticity, if they exceed the putative threshold of UE motor drive needed for recovery. Success Criteria: A significantly greater increase in FM of >4.25 points (the FM MCID40) between movable wheelchair arm rest device and control at three months.

At project end, we will have validated the clinical feasibility and efficacy of the movable wheelchair arm rest device and optimized it for production and mass distribution. If our plan is successful, we will have demonstrated that wheelchair-based "rocking therapy" can help patients routinely achieve the threshold level of sensory motor drive needed to provoke true UE recovery.

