## **Describe the primary outcome variable(s), secondary outcome variables, and predictors and/or comparison groups as appropriate for the stated study objectives/specific aims:**

### **Primary outcome measure**

The primary outcome measure will be the change in Fugl-Meyer Arm Motor Assessment Score (FMAMA) from baseline to three-month post-stroke to assess increases in motor recovery of the upper extremity.

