## **Describe the statistical methods for the stated specific aims and hypotheses. The analysis plans should match the stated study specific aims and hypotheses:**

All reported data from this study will be disaggregated by sex to test for any potential bias due to this biological variable. Data will be analyzed using modified intention-to-treat analysis. That is, all participants will be included in the analysis if the follow-up assessment is available, regardless of any deviations from the protocol. The effect of treatment on the primary outcome measure will be assessed using a repeated measures analysis of covariance (RM-ANCOVA) to account for any baseline differences between groups or variability in treatment intensity, with follow-up comparisons performed using Bonferroni-corrected t-tests or Wilcoxon rank sum tests if the data violates the assumption of normality. We hypothesize the participants in the movable wheelchair arm rest device group will have significantly greater and clinically meaningful (i.e. >4.25 FM points) reductions in motor impairment than participants in the control group due to the increased dose of UE motor system activation. Using data from the sensors on movable wheelchair arm rest device, we will test if this effect depends nonlinearly on the number of repetitions performed with the device, consistent with recent meta-analyses of forelimb recovery in a rodent model of stroke. That is, we hypothesize that the movable wheelchair arm rest device will provide a benefit only if the dose exceeds a threshold. A key goal is to also identify that threshold (by making a graph for humans like the one for rats), which will enable us to move forward with effective clinical prescription and goal setting with the movable wheelchair arm rest device. Visual analog pain, spasticity, and FAC scores will also be analyzed using RM-ANCOVA to test for significant changes related to use of the device. All analyses will be reviewed by a statistical consultant in the Institute for Clinical and Translational Science at UC Irvine.

**Provide precise definitions of the study endpoints and criteria for evaluation; if the primary outcomes are derived from several measurements (i.e., composite variables) or if endpoints are based composite variables, then describe precisely how the composite variables are derived:**

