The endpoint of the study is 3-month post-stroke follow up visit. The primary outcome measure is the Fugl-Meyer Upper Extremity Motor Assessment Score at the 3-month post-stroke follow-up.

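### The primary Fugl-Meyer endpoint and its test are each stated in two ways, no text says which governs, and the stated three-month target is tied to no model term

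*Combined protocol and SAP*

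**What the plan says.** **Endpoint.** The aims field under Background & Purpose of Research says "The primary outcome measure will be change in FM score from baseline to three-months post-stroke". The Primary outcome measure entry agrees: "The primary outcome measure will be the change in Fugl-Meyer Arm Motor Assessment Score (FMAMA) from baseline to three-month post-stroke". The field under Study Design & Statistics that asks for precise endpoint definitions says "The primary outcome measure is the Fugl-Meyer Upper Extremity Motor Assessment Score at the 3-month post-stroke follow-up".

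**Test.** The aims name RM-ANCOVA. The main statistical-methods field agrees: "The effect of treatment on the primary outcome measure will be assessed using a repeated measures analysis of covariance (RM-ANCOVA"), "with follow-up comparisons performed using Bonferroni-corrected t-tests or Wilcoxon rank sum tests if the data violates the assumption of normality". The next field, which asks for the method for the primary outcome, gives only "t-tests with Bonferroni corrections, or Wilcoxon rank sum tests if the distributions fail the Lilliefors test for normality". The field after that, for secondary or post hoc analyses, assigns a repeated-measures ANOVA, with no covariate mentioned, to each outcome measure.

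**Target.** The success criterion in the aims is a significantly greater FM gain, by more than 4.25 points, for device over control at three months. Sample Size Determination also powers the difference at the three-month follow-up.

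**Covariates.** RM-ANCOVA is chosen "to account for any baseline differences between groups or variability in treatment intensity". Project Procedures adds length of stay as a covariate in the data analysis, without saying in which model.

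**Status.** The renewal form reports that procedures are complete and analysis is under way.

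**The concern.** A confirmatory trial needs one endpoint, one test and one p-value fixed before results by arm are known. Here the fields that should fix the endpoint and the test each disagree with the text elsewhere. Three candidate analyses follow: a t-test on the three-month score, a t-test on change, and a baseline-adjusted model. The rank-sum variants and the unadjusted repeated-measures ANOVA add more.

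These can give different verdicts on the same data. If the choice is made after results are seen, the 5% error rate no longer holds. Read literally, the primary-method field also gives an unadjusted test, which is less precise than one adjusted for baseline FM. It divides alpha over an unstated number of comparisons.

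Treatment intensity and length of stay arise after randomisation. The plan attributes the expected benefit to a higher dose of arm activation, so adjusting the primary comparison for intensity could remove part of the effect under test.

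**Working it through.** **1. The plan's own figure.** 29 per group with 10% dropout leaves 29 × 0.90 = 26.1, so 26 per arm. In reverse, 26 / 0.90 = 28.9, rounded up to 29, and 2 × 29 = 58. Only this step can be reproduced. Effect size, SD, sidedness and the test used for power are not given, so 58 is neither confirmed nor refuted.

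**2. When the endpoint conflict matters.** Let y be the three-month FM, b baseline FM and g the arm. ANCOVA on change is y − b = a + τg + βb. Moving b across gives y = a + τg + (1 + β)b, with the same τ, standard error and p-value. One simulated data set confirmed this: both forms gave estimate 0.26157 and p = 0.21757. So the conflict has no effect where baseline is a covariate. It matters for the unadjusted tests.

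**3. Precision.** With equal SDs and baseline-to-three-month correlation ρ, the variances relative to the score t-test are 1 for the score, 2(1 − ρ) for change and 1 − ρ² for ANCOVA.
- ρ = 0.5: 1.00, 1.00, 0.75
- ρ = 0.7: 1.00, 0.60, 0.51

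**4. Disagreement between verdicts (simulation).** Assumed: normal data, equal SDs, ρ = 0.5 to 0.7, two-sided uncorrected 0.05, and single-time-point ANCOVA standing in for the three-month RM-ANCOVA contrast. The Wilcoxon branch is left out. The documents do not give ρ. The enrolled number comes from the renewal form: 2 + 12 + 23 = 37, taken as 19/18 with no dropout. The effect d is the three-month difference divided by the SD.

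| d | Three verdicts not all the same, 26/26 | Same, 19/18 | Change t-test vs ANCOVA only, 26/26 |
|---|---|---|---|
| 0.4 | 30-40% | 25-35% | 13-16% |
| 0.6 | 35-39% | 35-43% | 10-19% |
| 0.79 | 20-25% | 33-35% | 3-12% |
| 1.0 | 6-9% | 16-21% | 0-5% |

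At 19/18, change t-test and ANCOVA also disagree in no more than about 20%. With no effect, at least one of the three tests is significant in about 9-10% of trials. At 26/26 this is 6-7% if both t-tests use 0.025.

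**5. Share due to the raw-score t-test.** At d = 0.4, 26/26, subtract the change-versus-ANCOVA rate from the three-way rate.
- ρ = 0.5: 30.4 − 16.3 = 14.1 points, just under half
- ρ = 0.7: 40.4 − 13.5 = 26.9 points, about two thirds

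**6. Bonferroni.** For a two-sided t-test at 26 per arm, 80% power at 0.05 corresponds to d = 0.792 (noncentral t). At the same d, power is 71% at 0.05/2 and 65% at 0.05/3. With one comparison nothing is lost. The number of comparisons is an assumption.

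**The case against.** The best defence is that the main statistical text already gives an order, RM-ANCOVA first and t-tests or Wilcoxon tests as follow-up, and that the primary-method field only repeats the follow-up step. That is plausible, and the text as a whole leans that way. If it is right and baseline FM is a covariate, the change-versus-score conflict has no consequence. But the field that asks for the primary method leaves RM-ANCOVA out, and nothing says it is subordinate. The Bonferroni family stays undefined on either reading.

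A reader might infer that the target itself is open, and that an average over discharge and three months or a group-by-visit interaction could equally be the test. The documents do not support that. The success criterion and the sample-size text both fix the device-control difference at three months; only the model term is unnamed. Nor can a power figure be attached to the interaction, because it depends on whether baseline is a covariate or one of the three repeated visits, which is not stated.

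It is also fair to say that the three-way rates rest largely on the raw-score t-test, which is primary only if the endpoint-definition and primary-method fields are read together. The length-of-stay sentence does not say that it enters the primary model.

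The plan does provide a safeguard: "All analyses will be reviewed by a statistical consultant in the Institute for Clinical and Translational Science at UC Irvine". That is a review step, not a rule of precedence.

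**Conclusion.** The concern holds. Two endpoint definitions and two primary tests stand in the current text, with no precedence rule, no Bonferroni family and no model term linked to the stated three-month target. This should be settled before results are reported.

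The size is moderate and conditional on the assumed correlation, normality and proxy model. An open choice among the three tests roughly doubles the nominal 5% error. Verdicts differ in a third or more of trials at a moderate effect (d = 0.6). At the planned size, disagreement becomes uncommon at d = 1.0 (6-9%). At the enrolled 37 it is still about 16-21%, so a large effect would not make the choice immaterial. Between the change t-test and ANCOVA alone, disagreement stays at or below about 20%.

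Two further inferences go too far. The documents do not show that results by arm have been seen or that a test was chosen on them; they are silent on this. And the power loss under Bonferroni does not show that 58 was miscalculated, because it arises only if the primary-method field governs and covers more than one comparison.

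**What to change.** Use the same wording in the aims, the Primary outcome measure entry and the three statistical fields. The primary analysis is the device-minus-control contrast in FM at three months, adjusted for continuous baseline FM, as one test at two-sided 0.05, with no Bonferroni division and no normality pre-test.

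The smallest change is to name this as the three-month contrast within the existing RM-ANCOVA, with baseline FM as a covariate. The corresponding single-time-point ANCOVA would also serve.

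Then:
- State that the t-tests, Wilcoxon tests and repeated-measures ANOVA are secondary or sensitivity analyses, and that Bonferroni applies only to those follow-up comparisons.
- Keep treatment intensity and length of stay out of the primary model and use them only in a secondary one.
- Date the change and state whether results by arm had been seen. If they had, report the choice as post hoc and show the result under every reading.

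The cost is a wording change and a disclosure. No new data are needed.

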## Sample Size Determination:

1. Explain how the overall target sample size was determined (e.g., power analysis; precision estimation). Power analysis should (at least) match the primary outcome/endpoint.
2. Provide justification of the effect size for the primary outcome based on preliminary data, current knowledge/literature and/or cost consideration.
3. If appropriate, provide sample size justification for secondary outcomes.

Based on a power analysis using data from our previous LARA RCT with individuals with subacute stroke (n=19)36, enrolling 29 participants in each group, brings a total of 58 from 2 groups, will provide an 80% chance to demonstrate a significant difference in FM between the device and control at the three-month follow up ( $\alpha = 0.05$ ), assuming a dropout rate of 10%.

---

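### One section picks the primary FM test by a normality check on the trial's own outcome data, while other sections name RM-ANCOVA; after a switch no FM-point estimate is named for the 4.25-point criterion

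*Combined protocol and SAP*

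**What the plan says.** Four places in the combined protocol and SAP bear on the primary comparison.

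- **Statistical method(s) for the primary outcome(s) or endpoints:** Bonferroni-corrected t-tests, "or Wilcoxon rank sum tests if the distributions fail the Lilliefors test for normality". No covariate is mentioned. The answer that follows, on secondary or post hoc analyses, adds a repeated-measures ANOVA for each outcome measure.
- **Statistical methods for the stated specific aims and hypotheses:** the treatment effect on the primary outcome is assessed by RM-ANCOVA, with "follow-up comparisons performed using Bonferroni-corrected t-tests or Wilcoxon rank sum tests if the data violates the assumption of normality". The same answer expects the device to "provide a benefit only if the dose exceeds a threshold".
- **Background & Purpose of Research:** the p<0.05 hypothesis is tied to RM-ANCOVA. The success criterion is "A significantly greater increase in FM of >4.25 points" between device and control at three months.
- **Sample Size Determination:** "enrolling 29 participants in each group, brings a total of 58 from 2 groups, will provide an 80% chance", at alpha 0.05 with 10% dropout. No effect size or SD is given.

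Nowhere does the plan say which distributions the normality check uses (each arm, pooled data or residuals; score or change) or at what level. It does not say how many comparisons the Bonferroni correction covers. It names no estimate to accompany a Wilcoxon test.

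**The concern.** Two problems can be read off the text without any modelling.

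First, the sections give different primary analyses. One is a covariance model that can yield an adjusted difference in FM points. The other is a two-sample test with no stated adjustment, whose form depends on the outcome data. With the details of the check unstated, the analyst keeps a choice after seeing the data.

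Second, success is defined in FM points. A rank sum test addresses whether device scores tend to rank above control scores. It gives no mean difference or interval, so after a switch the p-value and the success criterion refer to different quantities.

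A third consequence is possible. If benefit appears only above a dose threshold, the device arm may be a mix of responders and non-responders. Such a mix can fail a normality test, and a rank test is weak when the gain sits in a minority. The trial could then lose power under the mechanism it proposes.

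**Working it through.** **1. The plan's own figure.** Expected analysed per arm: 29 × 0.90 = 26.1, so 26. The 29 per arm cannot be reproduced, because neither effect size nor SD is stated. Back-solving by the normal approximation (two-sided 5%, 80% power) gives d = (1.960 + 0.842) × √(2/26) = 0.777. If the target is 4.25 points, the implied SD is 4.25 / 0.777 = 5.47. This is an inference, not a figure in the plan.

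**2. Switch rate when both arms are exactly normal** (check at 5%, assumed):
- either arm fails: 1 − 0.95² = 9.75% (simulated about 10%)
- residuals tested once: 5%
- both arms must fail: 0.05² = 0.25%

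**3. Type I error.** In simulation (26 per arm, two-sided 5%) the two-stage rule rejects in 4.7-5.0% of null trials with per-arm testing and in at most 5.2% with residual testing.

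**4. Power under a threshold model.** 20,000 trials per scenario, before any Bonferroni step. Control is N(0, SD). Device is the same, plus a gain in a given share of users. Neither share nor SD is in the documents, so both are varied. With the mean effect held at 4.25 (gain = 4.25 / share), SD 5.47, and a switch if either arm fails:

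| Share responding | Gain | Switch rate | Fixed t-test | Two-stage rule |
|---|---|---|---|---|
| 15% | 28.3 | 87% | 35% | 16% |
| 25% | 17.0 | 34% | 51% | 43% |
| 35% | 12.1 | 13% | 60% | 58% |
| 50% | 8.5 | 10% | 68% | 67% |
| 75% | 5.7 | 10% | 75% | 75% |
| all | 4.25 | 10% | 79% | 79% |

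At a 25% share, SD 3 gives 73% against 35% and SD 8 gives 34% against 33%.

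**5. Dependence on how the check is read.** 30% of device users gain 20 points (mean effect 0.30 × 20 = 6.0):

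| SD | Fixed t-test | Either arm fails | Residuals tested | Both arms fail |
|---|---|---|---|---|
| 6 | 67% | 57% | 63-64% | 67% |
| 8 | 53.5% | 50.5% | 52.6% | 53.4% |

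At SD 10 the fixed t-test has 43% and the either-arm rule 41%.

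The renewal form reports 2 + 12 + 23 = 37 adults enrolled, about 18 per arm if split evenly. At 18 per arm (SD 6, 30% gaining 20) the fixed t-test has 49-50% and the either-arm rule 44-45%.

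**6. Cases that go the other way.** With right-skewed (gamma) changes, t-test against Wilcoxon power is 61% against 63% at a 50% share and 67% against 78% at a 75% share. In one illustrative bounded, bimodal model of the raw 3-month score (all inputs assumed), Lilliefors rejects in about 99% of trials with or without an effect, and Wilcoxon is stronger (41% against 29% at a 50% share).

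**7. Score or change.** The Background defines the outcome as change from baseline; the endpoint definition uses the 3-month score. With baseline FM as a covariate the choice does not matter. If Y − B = a + b·G + c·B, then Y = a + b·G + (c + 1)·B, with the same treatment coefficient b. An unadjusted t-test or Wilcoxon test lacks this property.

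**The case against.** The strongest reply is that RM-ANCOVA is the primary analysis and the t-test or Wilcoxon is only a follow-up. Two sections support that, and a covariance model can give the FM-point difference. This stands to the extent that Lilliefors selects the primary test only if the primary-outcome answer governs. It does not remove the problem. That answer responds directly to the question about the primary outcome, and the other section applies a normality-based switch to its follow-up comparisons.

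Two stronger inferences are tempting, and neither is supported.

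- *A reader might infer that the pre-test inflates false positives.* The simulations show type I error near 5%.
- *A reader might infer that the threshold hypothesis makes the rule switch more often and lose power as a matter of course.* The plan does not say that responders are a minority, and it gives no SD. At a 50% share or more with SD 5.47, the switch rate stays at its null value and the loss is under 1 point. The largest losses also assume that failure in either arm triggers the switch. The 17-point gain cited in the background is a between-group difference at five years, so it cannot be taken as a 3-month responder gain.

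It is also fair that Wilcoxon can be the better test for skewed or bounded scores, and that nothing bars the team from reporting a mean difference beside it. But no such estimate is named. That the better test depends on an unknown shape is a reason to decide in advance, not to let a noisy check decide.

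**Conclusion.** The point holds as one of pre-specification and estimand. The primary-outcome answer chooses its test from outcome data, conflicts with the RM-ANCOVA named elsewhere, and names no FM-point estimate after a switch. These conclusions rest on the text alone.

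The effect on power is conditional. In the SD 6 example it ranges from almost nothing to about 10 points, depending on the reading of the check. It can be larger with a smaller responding share or a smaller SD, and it is negligible when half or more of the device arm respond at SD 5.47. It may reverse for skewed or bounded scores. Share, gain, SD, the 5% level of the check and two-sided testing are assumptions. The change should be made, but the case for it does not depend on the threshold model.

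**What to change.** 1. Delete the Lilliefors condition from the primary-outcome answer and the normality condition from the aims-and-hypotheses answer.
2. Reconcile these sections and the Background by naming one primary analysis: the device-minus-control difference in 3-month FM, adjusted for baseline FM, with its 95% CI and a heteroscedasticity-robust standard error. Set that estimate against the 4.25-point criterion. A single primary contrast needs no Bonferroni step.
3. Report Wilcoxon only as a labelled sensitivity analysis that cannot replace the primary result.
4. Date the change and state whether outcomes by arm had been seen. The renewal form says that enrolment and follow-up are complete and analysis is under way.

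The cost is SAP wording; baseline FM is already collected. The downside is that for some skewed or bounded outcomes a rank-based test would have had more power.
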